#### **5.4. Prior and Concomitant Medications**

Currently, no drugs are contraindicated for co-administration with emtricitabine. Investigators should refer to the product/package inserts of the other antiretroviral medications for contraindications related to their use.

## 6. STUDY PROCEDURES

### 6.1. Subject Enrollment and Treatment Assignment

Before enrolling in this study, subjects must have completed through at least 96 weeks on the FTC-203 study and complete the End-of-Study Visit procedures for FTC-203 (see Section 6.2.1 and Appendix 2 hereinafter for details). The subject's parent(s) or other legal guardian(s) must then provide written informed consent for him (or her) to participate in the rollover protocol. Where applicable, depending on the age of the subject and prevailing institution practice regarding consenting minors, consent or assent may also be obtained from the subject. Subjects who participate in this rollover protocol must meet the inclusion criteria detailed in Section 4.2. To ensure uninterrupted treatment with the study drug, emtricitabine, if there is a reasonable expectation that the subject will meet the virologic criteria set out in Section 3.1, based on the results of HIV-1 RNA viral load testing performed at previous FTC-203 clinic visits, the End-of-Study Visit for the FTC-203 study and the Baseline visit of the rollover protocol can and should be completed at the same clinic visit, with the subject receiving his first supply of emtricitabine through the rollover protocol at that visit.

### 6.2. Study Assessments

#### 6.2.1. End-of-Study Visit (FTC-203)/Baseline Visit (GS-US-162-0112)

For the End-of-Study Visit for the FTC-203 study, the following procedures will be completed:

- Record height (or length) and body weight.
- Perform a physical examination.
- Obtain vital signs.
- Obtain blood and urine samples for the following laboratory evaluations: CD4+ cell count, plasma HIV-1 RNA level, plasma for storage, hematology, chemistry and urinalysis
- Female subjects of childbearing potential must have a urine pregnancy test performed. If the urine pregnancy test is positive, a serum  $\beta$ -HCG test should be performed and the GSI Medical Monitor contacted.
- Record HIV-1 related events, adverse events, and concomitant medications.
- Complete drug accountability, including ensuring that all previously unused FTC-203 study medications(s), *i.e.*, the study drug, emtricitabine, and, where applicable, the

lopinavir-ritonavir and stavudine provided for ART-naïve subjects, is/are returned by the subject.

The following procedures will be completed as part of the Baseline Visit for the GS-US-162-0112 rollover protocol:

- Obtain written informed consent from parent or other legal guardian and, where applicable, the subject.
- Review inclusion criteria for the rollover protocol.
- Record height (or length) and body weight.
- Review adverse events.
- Complete drug accountability and provide a new supply of the study drug, emtricitabine for the rollover protocol.

Procedures required at both the End-of-Study Visit for FTC-203 and the Baseline Visit will not need to be repeated if done at the same clinic visit. However, information may need to be recorded in the CRFs of both studies.

Genotypic analysis may be performed for subjects to determine whether they are eligible to participate in the rollover protocol. If needed, genotypic analysis will be performed by the Clinical Virology and Diagnostics group, GSI (Durham). As necessary, each study center should contact the GSI Clinical Program Manager responsible for the rollover protocol to request approval for genotypic analysis, as well as sample collection and shipping instructions to the GSI Durham office.

### **6.2.2.        Clinic Visits**

During the rollover protocol, clinic visits will occur every 12 weeks. At each visit, the Investigator will manage each subject's care according to current "standard of care" practices at his (or her) institution, complete drug accountability and provide the subject with a new supply of emtricitabine. Each Subject will continue to receive the study drug, emtricitabine, for as long as they continue to meet the following virologic criteria, either:

- they have a plasma HIV-1 RNA viral load of  $\leq 400$  copies/mL, or
- if the subject's plasma HIV-1 RNA viral load is  $> 400$  copies/mL, their viral load is  $< 1.0 \log_{10}$  above the nadir recorded after Week 8 of the FTC-203 study and there is reliable genotypic evidence showing a lack of resistance to emtricitabine.

At each clinic visit, the Investigator (or designee) will measure the child's height (or length) and weight, and assess adverse events, but only those AEs that (1) meet the criteria for an

SAE, (2) that result in permanent discontinuation of the study drug, emtricitabine, and/or (3) are associated with skin discoloration (hyperpigmentation) will be recorded in the subject's CRF. Non-serious AEs that do not result in the discontinuation of emtricitabine and/or are not associated with skin discoloration (hyperpigmentation), the results of routine clinical laboratory testing (hematology, clinical chemistry and urinalysis), immunological data (absolute and percent CD4+), pregnancy test results, and physical examination findings collected in the FTC-203 study will no longer be collected or recorded in their CRF, nor will the findings of any assessments done according to current standard of care practices be recorded in the CRF. Information relating to the dispensing and accountability of the study drug will be recorded in the CRF.

### **6.3. Assessments for Premature Discontinuation From Study**

If a subject discontinues the study drug, emtricitabine, regardless of reason, the Investigator should assess all reported AEs and complete drug accountability. Any AE(s) that led to the permanent discontinuation of study drug should be recorded in the CRF. The subject must return all unused study drug to the study center.

#### **6.4. Criteria for Suspension of Study Drug**

Subjects who do not maintain plasma HIV-1 RNA levels as outlined in Section 6.2.2 above must be discontinued from study drug. Furthermore, the study drug, emtricitabine, may be discontinued in the following instances:

- Upon approval for market distribution in South Africa (and the subject has means to access the drug).
- Unacceptable emtricitabine-related toxicity necessitating the permanent discontinuation of study drug. Brief (generally  $\leq$  14 days) interruptions in treatment are permitted, *e.g.*, to manage a newly emergent toxicity. Longer ( $>$  14 days) interruptions are permitted only with the approval of the GSI Medical Monitor and will be decided on a case-by-case basis.
- Subject request to discontinue for any reason.
- Subject non-compliance (in the judgment of the Investigator or Sponsor).
- Subject pregnancy.
- In the judgment of the Investigator or Sponsor, it is not considered to be in the subject's best interest (for whatever reason) to continue in the rollover protocol.
- Discontinuation of the rollover protocol at the request of GSI, applicable regulatory agency(ies) or IEC.

## 7. ADVERSE EVENTS AND TOXICITY MANAGEMENT

### 7.1. Adverse Events

An adverse event (AE) is any untoward medical occurrence in a clinical investigation subject administered a medicinal product and which does not necessarily have a causal relationship with this treatment. An AE can therefore be any unfavorable and unintended sign, symptom, or disease temporally associated with the use of a medicinal product, whether or not considered related to the medicinal product. AEs may also include pre- or post-treatment complications that occur as a result of protocol-mandated procedures (*e.g.*, invasive procedures such as venipuncture, biopsy, *etc.*). Pre-existing events, which increase in severity or change in nature during or as a consequence of use of a medicinal product in human clinical trials, will also be considered AEs.

An AE does not include:

- Medical or surgical procedures (*e.g.*, surgery, endoscopy, tooth extraction, transfusion); the condition that leads to the procedure is an AE.
- Pre-existing diseases or conditions or laboratory abnormalities present or detected prior to study entry that do not worsen.
- Situations where an untoward medical occurrence has not occurred (*e.g.*, hospitalization for elective surgery, social and/or convenience admissions).
- Overdose of either the study drug, emtricitabine, or a concomitant medication without any signs or symptoms unless the subject is hospitalized for observation.

### 7.2. Assessment of Adverse Events

AEs that (1) meet the criteria for a serious adverse event (SAE) (as defined in Section 7.3), (2) lead to permanent discontinuation of the study drug, emtricitabine, and/or (3) are associated with skin discoloration (hyperpigmentation) will be assessed by the Investigator and recorded on the appropriate CRF page, including the date of onset and resolution, severity, relationship to study drug or study procedures, emtricitabine, outcome and action taken with the study drug. No other AEs will be recorded.

Severity should be recorded and graded according to the GSI-modified DAIDS/NIAID Common Toxicity Grading Scale (see Appendices 3 and 4 to this protocol). The relationship to the study drug, emtricitabine, or study procedures should be assessed using the following definitions:

- **No:** Evidence exists that the AE has an etiology other than the study drug or study procedures (e.g., pre-existing condition, underlying disease, intercurrent illness, or concomitant medication).
- **Yes:** A temporal relationship exists between the event onset and administration of the study drug or between the event and the study procedures. It cannot be readily explained by the subject's clinical state or concomitant therapies and, in the case of the study drug, appears with some degree of certainty to be related, based on the known therapeutic and pharmacologic actions or AE profile of the study drug. In case of cessation or reduction of the dose, the event abates or resolves and reappears upon re-challenge. It should be emphasized that ineffective treatment should not be considered as causally related in the context of AE reporting.

These criteria in addition to good clinical judgment should be used as a guide for determining the causal assessment. If it is felt that the event is not related to the study drug, then an alternative explanation should be provided.

### 7.3.                   **Serious Adverse Events**

A SAE is defined as follows:

Any adverse drug experience occurring at any dose that results in any of the following outcomes:

- Death;
- Life-threatening situation (subject is at **immediate** risk of death);
- In-patient hospitalization or prolongation of existing hospitalization (excluding those for study therapy or placement of an indwelling catheter, unless associated with other serious events);
- Persistent or significant disability/incapacity;
- Congenital anomaly/birth defect in the offspring of a subject who received study drug;
- Other: medically significant events that may not result in death, be immediately life-threatening, or require hospitalization, may be considered a SAE when, based upon appropriate medical judgment, they may jeopardize the subject and may require medical or surgical intervention to prevent one of the outcomes listed in this definition.

Examples of such events are:

- Intensive treatment in an emergency room or at home for allergic bronchospasm
- Blood dyscrasias or convulsions that do not result in hospitalization

- Development of drug dependency or drug abuse.

### **Clarification of Serious Adverse Events**

- Death is an outcome of an AE, and not an AE in itself. In reports of death due to “Disease Progression”, where no other information is provided, the death will be assumed to have resulted from progression of the disease being treated with the study drug.
- All deaths, regardless of cause or relationship, must be reported for subjects on study and for deaths occurring within 30 days of last study drug dose or within 30 days of last study evaluation, whichever is longer.
- “Occurring at any dose” does not imply that the subject is receiving study drug at the time of the event. Dosing may have been given as treatment cycles or interrupted temporarily prior to the onset of the SAE, but may have contributed to the event.
- “Life-threatening” means that the subject was at immediate risk of death from the event as it occurred. This does not include an event that might have led to death, if it had occurred with greater severity.
- Complications that occur during hospitalizations are AEs. If a complication prolongs hospitalization, it is a SAE.
- “In-patient hospitalization” means the subject has been formally admitted to a hospital for medical reasons, for any length of time. This may or may not be overnight. It does not include presentation and care within an emergency department.
- The Investigator should attempt to establish a diagnosis of the event based on signs, symptoms and/or other clinical information. In such cases, the diagnosis should be documented as the AE and/or SAE and not the individual signs/symptoms.

A distinction should be drawn between serious and severe AEs. An AE that is assessed as grade 4 (potentially life-threatening) should not be confused with a SAE. Severity is a category utilized for rating the intensity of an event; and both AEs and SAEs can be assessed as grade 4.

#### **7.4.                   Serious Adverse Event Reporting Requirements**

##### **7.4.1.               All Serious Adverse Events**

GSI has requirements for expedited reporting of SAEs meeting specific requirements to worldwide regulatory authorities; therefore, GSI must be notified immediately regarding the occurrence of any SAE that occurs after the screening (initial) visit, including SAEs resulting

from study procedures performed from screening onwards. The procedures for reporting all SAEs, regardless of causal relationship, are as follows:

- Record the SAE on the AE CRF and complete the “Serious Adverse Event Report” form.
- Fax the SAE report to the attention of the GSI Global Drug Safety Department (GDS) within 24 hours of the Investigator’s knowledge of the event. GDS contact information is provided below.
- For fatal or life-threatening events, also fax copies of hospital case reports, autopsy reports, and other documents when requested and applicable.

GSI Global Drug Safety: Name:

PPD

Manager, GDS

Telephone:

PPD

(Working Days)

Fax:

PPD

Email:

PPD

GSI Medical Monitor:

Name:

[name].

Sr. Clinical Research Physician, Clinical Research

Telephone:

PPD

(Working Days) /

Cellphone:

PPD

(Medical Emergencies)

Fax:

PPD

Email:

PPD

GSI may request additional information from the Investigator to ensure the timely completion of accurate safety reports.

The Investigator must take all therapeutic measures necessary for resolution of the SAE. Any medications necessary for treatment of the SAE must be recorded onto the concomitant medication section of the subject’s CRF.

Follow-up of AEs will continue through the last day on study (including the follow-up, off study drug period of the study), until the Investigator and/or GSI determine that the subject’s condition is stable, or up to 30 days after the last dose of study drug, whichever is longer. GSI may request that certain AEs be followed until resolution.

#### **7.4.2. Investigator Reporting Requirements for SAEs**

A SAE may qualify for reporting to regulatory authorities if the SAE is possibly attributable to the study drug, and is unexpected based upon the current Company Core Safety Information appended to the emtricitabine Investigator’s Brochure. In this case, all Investigators will receive a formal notification describing the SAE.

The Investigator should notify the Independent Ethics Committee (IEC) as soon as is practical, of serious events in writing where this is required by local regulatory authorities, and in accordance with the local institutional policy.

#### **7.4.3. Post Study Reporting Requirements**

All deaths, regardless of cause or relationship, must be reported for subjects on study and for all deaths occurring within 30 days of last study drug dose.

#### **7.5. Clinical Laboratory Abnormalities and Other Abnormal Assessments as Adverse Events or Serious Adverse Events**

Clinical laboratory abnormalities (*e.g.*, clinical chemistry, hematology or urinalysis) or other abnormal findings (*e.g.*, electrocardiogram, X-rays or vital signs) performed as part of current standard of care should not be recorded as adverse events in the CRF unless serious and/or they lead to the discontinuation of study drug, emtricitabine. Wherever possible, the Investigator should attempt to establish a diagnosis of the event, based on signs, symptoms and/or other clinical information. In such cases, the diagnosis should be documented as the AE and/or SAE and not the individual signs/symptoms. The results of routine clinical laboratory (hematology, clinical chemistry and urinalysis), immunological data (absolute and percent CD4+), pregnancy test results, and physical examination findings collected in the FTC-203 study will no longer be collected or recorded in the CRF, nor will the findings of any assessments done according to current standard of care practices during the rollover protocol be recorded in the CRF.

#### **7.6. Toxicity Management**

Clinical events that meet the criteria for an SAE and/or that lead to discontinuation of the study drug, emtricitabine, will be graded according to the GSI-modified DAIDS/NIAID Common Toxicity Grading Scale (see Appendices 3 and 4). The relationship to study drug or study procedures will be assessed using the definitions outlined in Section 7.2.

For any toxicity, Investigators are urged to identify the drug most likely to be the cause of the toxicity and change that drug or dosage, if possible. To manage specific toxicities associated with background antiretroviral medications, the Investigator should follow the current package insert, manufacturer's guidelines and/or Investigator's Brochure for the individual drugs. If a subject becomes intolerant to emtricitabine, the decision to interrupt, dose adjust and/or discontinue the medication must be promptly communicated to the GSI Medical Monitor. Brief (generally  $\leq$  14 days) interruptions in treatment are permitted, *e.g.*, to manage a newly emergent toxicity. Longer ( $>$  14 days) interruptions are permitted only with the approval of the GSI Medical Monitor and will be decided on a case-by-case basis. The GSI Medical Monitor will be available for consultation on all toxicity-related issues (see Section 7.4.1 for contact information).

## 7.7. Major Toxicities of Emtricitabine

The most common side effects seen in subjects treated with emtricitabine in combination with other anti-HIV drugs are: allergic reaction, headache, dizziness, insomnia, abnormal dreams, diarrhea, nausea, vomiting, problems with digestion resulting in gastrointestinal discomfort after meals, abdominal pain, rash, changes in skin color on the palms and/or soles, pain, feeling tired or weak, increased triglycerides levels, adverse effects on the function of the liver (*e.g.*, elevated bilirubin), and pancreas, increased blood glucose, and low white blood cell count. Increases in creatine kinase, associated with muscle pain and weakness, have also been reported. Anemia has been reported in pediatric subjects treated with emtricitabine.

See the emtricitabine Investigator's Brochure for more detailed information.

### 7.7.1. Skin Discoloration

In the adult clinical trials, skin discoloration was reported more frequently in patients treated with emtricitabine, as compared to patients enrolled in control groups [{7095}](#). The skin discoloration occurred as hyperpigmentation, most commonly on the palms and/or soles, and was always mild or moderate, generally asymptomatic and without association with any pathologic skin condition.

In the event that a subject should develop hyperpigmentation while participating in this rollover protocol, the hyperpigmentation should be documented in the CRF as an adverse event and a Hyperpigmentation Assessment CRF completed. In addition, the subject may be required to have one or more dermatological consultations and possibly other explorations, as deemed necessary by the dermatologist. Any relevant medical consultation should be retained in the study files and appended to the subject's CRF.

## 7.8. Risks for Women of Childbearing Potential or During Pregnancy

The risks of treatment with the study drug, emtricitabine, during pregnancy have not been evaluated. Animal studies do not indicate direct or indirect harmful effects of emtricitabine with respect to pregnancy. Please refer to the latest version of the Investigator's Brochure for additional information. Barrier contraception should always be used in combination with other methods of contraception (*e.g.*, oral or other hormonal contraceptives) by females of child bearing potential who are less than 2 years post-menopausal while participating in the study and for 30 days following the last dose of study drug. Male subjects in the study who are sexually active must use barrier contraception for the same period of time with their female partners of childbearing potential or agree to abstain from heterosexual intercourse for the duration of their participation in the study.

The subject must be instructed to discontinue the study drug (and other medications, as applicable) and inform the Investigator **immediately** if she becomes pregnant during the study.

The Investigator should report all pregnancies to the GSI within 24 hours of becoming aware of the pregnancy. The Investigator should counsel the subject regarding the possible effects of prior study drug exposure on the fetus and the need to inform the study center of the outcome of the pregnancy.

Any pregnancy complication or elective termination of a pregnancy for medical reasons will be recorded as an SAE. A spontaneous abortion is always considered to be an SAE and will be reported as described in the AE and SAE sections. Furthermore, any SAE occurring as an adverse pregnancy outcome post-study must be reported to GSI.

Additionally all pregnancies that occur during the study should be reported using the Pregnancy Report CRF page. Monitoring of the subject should continue until the conclusion of the pregnancy. The outcome should be reported to GSI using the Pregnancy Outcome (and Abnormal Pregnancy Outcome, if applicable) CRF page(s). If the end of the pregnancy occurs after the study has been complete, the outcome should be reported directly to GSI. Pregnancies that occur after the subject has discontinued study drugs do not require monitoring.

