### 4.2. Inclusion Criteria

To participate in the rollover protocol, each subject must meet *all* of the following inclusion criteria:

- Complete or have previously completed at least through the Week 96 Visit (*i.e.*, 96 weeks on study) for the FTC-203 study.
- Complete all End-of-Study Visit procedures for the FTC-203 study.
- Either (a) have a plasma HIV-1 RNA viral load of  $\leq 400$  copies/mL at the End-of-Study Visit for the FTC-203 study, or (b) if the subject's plasma HIV-1 RNA viral load at the End-of-Study Visit for FTC-203 study is  $> 400$  copies/mL, their viral load is  $< 1.0 \log_{10}$  above the nadir recorded after Week 8 of the FTC-203 study and there is reliable genotypic evidence showing a lack of resistance to emtricitabine.
- A parent or other legal guardian has provided written informed consent to the subject participating in the rollover protocol. As applicable, based on the subject's age and normal institution practice, the subject should additionally provide their written informed consent or assent to participate in the rollover protocol.
- If a female of childbearing potential has a negative serum beta-human chorionic gonadotropin ( $\beta$ -HCG) test at the End-of-Study Visit for the FTC-203 study.
- If sexually active (male and female) and/or of childbearing potential, be willing to use an effective method of contraception while enrolled in the study and for a period of at least 1 month after the last dose of emtricitabine. Acceptable methods of contraception include an intra-uterine device or barrier contraceptives (*i.e.*, cap/diaphragm, male condom, female condom, *etc.*) with a spermicide. Because the effects of emtricitabine on hormonal contraceptives have not been characterized, oral and depot contraceptives (*i.e.*, implant or injectable) must be used in conjunction with an acceptable barrier contraceptive. See Section 7.8 for more information on contraception and pregnancy.

- Have no medical condition or any other set of circumstances, which, in the opinion of the Investigator or Sponsor, means that it would not be in the best interests of the subject to participate in the rollover protocol and/or continue treatment with emtricitabine.

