2.4. Analysis Windows

Study Day 1 is defined as the day when the first dose of study drug in this study, as recorded on the study drug accountability case report form. Baseline visit is defined as the Study Day 1 visit.

Study Day is calculated relative to Study Day 1. For events that occurred on or after Study Day 1, Study Day is calculated as (visit date minus date of the first dose plus 1). For events that occurred prior to Study Day 1, Study Day is calculated as (visit date minus date of the first dose).

Subject visits might not occur on protocol-specified days. Therefore, for the purpose of analysis, observations will be assigned to analysis windows.

The analysis windows (for height, weight, AE visits, etc) are presented in Table 2-1.

Table 2-1. Analysis Windows

	Nominal Day	Visit Window
Baseline		≤ 1
Week 12	84	[2, 126]
Week $12*k$, $k = 2, 3, \dots, 43$	$84*k$	[$84*k-41, 84*k+42$]

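### Protocol Section 7.8 ends the male abstinence option with study participation, while the barrier option in the same sentence, and Section 4.2, run about a month past the last dose

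*Protocol*

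**What the plan says.** Protocol Section 7.8 first sets the period for females of childbearing potential, who are to use contraception "while participating in the study and for 30 days following the last dose of study drug". It then turns to males: "Male subjects in the study who are sexually active must use barrier contraception for the same period of time". The reference is back to the female period, so the male barrier option covers participation plus 30 days. The same sentence offers an alternative, "or agree to abstain from heterosexual intercourse for the duration of their participation in the study".

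Section 4.2 (Inclusion Criteria) has its own rule. Subjects of either sex who are sexually active, and those of childbearing potential, must be willing to use effective contraception "while enrolled in the study and for a period of at least 1 month after the last dose of emtricitabine". On methods it says: "Acceptable methods of contraception include an intra-uterine device or barrier contraceptives", taken with a spermicide, and it requires a barrier alongside hormonal methods. Abstinence is not mentioned.

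**The concern.** Two alternatives offered for the same protection should last equally long unless a reason is given, and none is. The sponsor chose a 30-day post-dose window and applied it to females and to males who use barriers. The males who choose abstinence are the only group whose obligation stops earlier. A site that counsels from Section 7.8 alone would give them the shorter date.

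What is at stake is the protection of partners and pregnancies in the weeks after dosing stops. Section 7.8 says that the risks of emtricitabine in pregnancy have not been evaluated, and also that animal studies do not indicate harm. Nothing in the SAP's listings or summaries depends on this point.

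**Working it through.** The plan has no figure to reproduce here. The check compares the stated periods and then sizes the gap.

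**Post-dose cover, by text**

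| Rule | Source | Cover stated after last dose |
|---|---|---|
| Females of childbearing potential | Protocol 7.8 | 30 days |
| Males, barrier | Protocol 7.8, by reference to the female period | 30 days |
| Males, abstinence | Protocol 7.8 | none stated |
| Sexually active males and females, contraception | Protocol 4.2 | at least 1 month |

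**Does participation already include the 30 days?** The protocol's usage points the other way.

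- Section 7.8 joins participation and the 30 days with *and*. The second part would add nothing if the first always contained it.
- Section 7.4.3 makes the same split for another purpose: deaths "must be reported for subjects on study and for all deaths occurring within 30 days of last study drug dose".
- Section 7.4.1 mentions an off-drug follow-up period, but gives it no length. Section 6.3 asks only for adverse event assessment and drug accountability and return at discontinuation, and Appendix 2 schedules no visit after that.

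**Size of the gap.** Let d be the days of participation after the last dose. The protocol does not state d; I assume 0 to 30.

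Shortfall = 30 − d days

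- d = 0: 30 − 0 = 30 days
- d = 30: 30 − 30 = 0 days

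**Does Section 4.2 close the gap?** Only in part. It is an inclusion criterion, reviewed at the Baseline Visit (Section 6.2.1 and Appendix 2), and for males it applies to those sexually active. FTC-203 enrolled children from 3 months to 17 years of age (Section 1.2), and follow-up here can be long. SAP Section 2.4 says: "The analysis windows (for height, weight, AE visits, etc) are presented in Table 2-1". That table runs to k = 43:

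- 12 × 43 = 516 weeks
- 84 × 43 = 3612 days, and 3612 / 365.25 = 9.9 years

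A boy who was not sexually active at entry can become so over that time. The rule then written for him is Section 7.8. The table shows how long follow-up may last; it has no bearing on the post-dose gap itself.

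**The case against.** The strongest reply is that the rule for a sexually active male is not short. Section 7.8 says such males "must use barrier contraception for the same period of time with their female partners of childbearing potential", and Section 4.2 asks for at least 1 month. A male who ends his abstinence inside the 30 days is sexually active again, so the two sections read together would expect him to use a barrier. That is a sensible reading of intent, but the text does not say it. The sentence addresses males in the study and offers two alternatives; one who abstained throughout has met it in full, and nothing revives the barrier duty afterwards.

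Other points limit the size, and they stand:

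- The chain of events is narrow. A male must choose abstinence over a barrier, stop drug, and then have unprotected intercourse within 30 days.
- Some subjects will not stop emtricitabine when study supply ends. Section 6.4 allows discontinuation on market approval where the subject can obtain the drug, and a subject who moves to commercial supply has no washout at that point.
- Because participation is not defined, 30 days is a maximum.
- The death-reporting rule and the SAP windows are indirect support. The mismatch within Section 7.8 carries the argument without them.
- Consent pages were not available for review, so the gap can be claimed only for the protocol body.

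**Conclusion.** The inconsistency is real and minor. Within one sentence of Section 7.8, the barrier option ends 30 days after the last dose and the abstinence option ends with participation. Section 4.2 does not settle the matter, because it does not name abstinence and is checked at entry.

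The shortfall is 30 days if participation ends with dosing, and anywhere down to 0 under the assumed range for time off drug. The number of males affected cannot be derived from the documents and is probably small. The conclusion rests on reading participation and the post-dose window as separate periods, as Section 7.8 itself does. It is worth correcting when the protocol is next opened, and does not call for an amendment of its own.

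**What to change.** Extend the abstinence clause in Section 7.8 so that it runs through participation and for at least 30 days (1 month) after the last dose of study drug. Both male options then end together and agree with Section 4.2. If the sponsor wants a single expression throughout, the 30 days in the female and barrier rules of 7.8 and the 1 month in 4.2 should be put in the same words at the same time.

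The cost is one clause at the next amendment, with no added visit, test or CRF page. Males who choose abstinence take on up to 30 more days of commitment, and the barrier option stays open to them. The change may come too late for subjects who have already left the study.
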